This SAP is not used for other analyses or other studies. It is based on the Study Protocol (CSP), Version 02 (Amendment 2) dated 30-Nov-2022.

1.1 Study design

This study is a 52-week, randomized, open-label, multi-center, two-arm study for pretreated patients with suboptimal anatomically controlled nAMD.

Consenting patients will participate in a screening period, lasting up to 14 days. Eligible patients will be randomized in a 1:1 ratio to one of the two treatment arms:

- Brolucizumab 6 mg “loading arm”: 3 x 4-weekly initial injections followed by an injection every 12 weeks
- Brolucizumab 6 mg “non-loading arm”: one initial injection followed by an injection every 12 weeks

There are three periods in this study (see Figure 1.1):

- Screening period: from day -14 to Baseline
- Open-label treatment period: from Baseline (day 1) to week 48
- Post-treatment follow-up period: from week 48 to week 52

[figure not shown]

Figure 1.1 Study Design

1. Screening period: Day-14 to day -1

A screening period of up to 2 weeks will be used to assess eligibility.

One time rescreening of patients is allowed, except for the purpose of capturing new BCVA or imaging assessments that previously failed to qualify the patient. As long as testing can be repeated within 14 days of the first screening, the other screening assessments do not need to be repeated. If rescreening is to occur beyond 14 days from the original screening visit date, then all screening procedures must be repeated. Medical judgment should be exercised to ensure that treatment of nAMD is not withheld in order for a patient to participate in the study.

2. Open-label treatment period: Day 1 to Week 48

After confirmation of eligibility, patients will be randomized in a 1:1 ratio to one of the treatment arms.

Only one eye will be selected as study eye and treated with study medication.

The baseline visit is defined as Day 1/Visit 1, and end of treatment visit as Visit 13 (Week 48).

A study visit schedule will be established at the time of randomization for all patients with study visits scheduled every 4 weeks. All efforts should be made to adhere to this study visit schedule ± 7 day window. Treatment is intended to be administered on the day of study visit, or if this is not possible, within 3 days after the study visit when the per-protocol assessments took place. In addition, for a given protocol visit, assessments can be performed on two consecutive days.

In the “loading arm”, patients will receive three consecutive injections every 4 weeks at baseline, weeks 4 and 8, which should be at least 21 days apart, followed by an injection every 12 weeks. In the “non-loading arm”, patients will receive one initial injection followed by an injection every 12 weeks. For both study arms the assessment of disease activity will be performed 8 and 12 weeks after the previous injection. If disease activity is identified by the investigator for the first time at any visit after / from week 8 respectively, patients should stay on a q12w dosing, if the decline in BCVA is clinically non-significant (BCVA loss < 4 ETDRS letters) compared to the previous visit. If after / from week 8 BCVA-loss of ≥ 5 ETDRS letters appears compared to the previous visit or disease activity is identified for a second time based on the investigator’s judgment of visual and / or anatomic outcomes and signs of disease activity, patients must be assigned to q8w dosing. One attempt of interval re-extension from q8w to q12w treatment will be allowed based on the investigator’s judgement if no disease activity (DA) is detected during the subsequent visit(s). If the patient shows significant DA at any visit after the re-extension attempt, injection intervals will be fixed to q8w until the end of the study.

Patients who require injections more frequently than every 8 weeks after the loading phase (week 8, loading arm) or baseline (non-loading arm) will be discontinued from further study treatment.

3. Post-treatment follow-up period: Week 48 to week 52

For all patients, the last study assessment will be performed at week 52.

Patients withdrawn from the study prior to study completion will be asked to return for an early discontinuation visit (EOS / Visit 14), four weeks (± 7 days) following their last study visit.

1.2 Study objectives and endpoints

This study is designed as a randomized, open-label, multi-center, two-arm parallel study to assess the efficacy and safety of two different brolucizumab 6 mg regimen for pretreated patients with suboptimal anatomically controlled nAMD.

The primary objective of this study is to evaluate descriptively the difference of brolucizumab 6 mg with one (initial) injection followed by q12w maintenance as compared to brolucizumab 6 mg with 3x q4w loading injections followed by q12w maintenance with respect to the change in BCVA from baseline to mean of visits at week 40 to week 52.

Table 1.1 Objectives and related endpoints

Objective(s)	Endpoint(s)
Primary Objective(s) To evaluate the difference of brolucizumab 6 mg with one (initial) injection followed by q12w maintenance as compared to brolucizumab 6 mg with 3x q4w loading injections followed by q12w maintenance	Endpoint(s) for primary objective(s) 
Mean change in BCVA from baseline to mean of visits at week 40 to week 52
Secondary Objective(s) 
1. To evaluate treatment interval prolongation compared to previous treatment2. To estimate the proportions of patients maintained at q12w treatment frequency in the two brolucizumab groups3. To evaluate the functional outcomes comparing the two brolucizumab groups4. To evaluate the anatomical outcomes comparing the two brolucizumab groups	Endpoint(s) for secondary objective(s) 
Mean treatment interval (overall as well as per study group comparing treatment intervals from week 8 to week 52 in the study vs. 24 weeks to baseline prior to enrollment)Rate of patients (overall and per group) with prolonged interval compared to mean treatment interval in last 24 weeks prior to enrollmentComparison of proportions of patients maintained at a q12w interval from baseline / upload to week 52 between the two armsDistributions of patients at q8w/q12w intervals from baseline to week 52Average change in BCVA from baseline to week 52Proportion of patients with BCVA improvements of ≥ 5, ≥ 10, and ≥ 15 letters from baseline to week 52Proportions of BCVA ≥ 69 letters at week 52Mean change in BCVA from baseline to mean of visits at week 16 to week 28Change from baseline in CST as assessed by SD-OCT per visit up to week 52Absence of IRF, SRF, and sub-RPE fluid as assessed by SD-OCT per visit up to week 52

Objective(s)	Endpoint(s)
5. To evaluate the safety and tolerability of brolucizumab	
• Presence of active CNV leakage as assessed by fluorescein angiography at week 52• Incidence of Ocular and Non-ocular AEs up to Week 52

2 Statistical methods

2.1 Data analysis general information

The primary safety and efficacy analysis will be based on all subject data at the time the trial ends. This analysis will be performed once all patients completed their final visits or terminated the study prematurely.

2.1.1 General definitions

The term study treatment is used for Brolucizumab 6 mg/0.05 mL.

The baseline visit is defined as day 1/visit 1.

The on-treatment period lasts from the date of first administration of study treatment to 30 days after the last administration of study treatment (EOT) or EOS whichever is the latest.

Calculation of treatment interval:

- “Mean treatment interval from week 8 to week 52”: (last injection – first injection from week 8 on*) divided by (number of injections from week 8 to week 52 -1)

*the first injection from week 8 on could be at week 8 or later.

- “Mean treatment interval in last 24 weeks prior to first brolucizumab injection” will be calculated as: (date of first brolucizumab injection - date of first anti-VEGF pre-treatment within last 24 weeks) divided by number of injections within 24 weeks prior to first brolucizumab injection.

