4.2 Rationale for dose/regimen and duration of treatment

The dose and different regimens for brolucizumab are based on the following considerations:

- Brolucizumab is well tolerated at a dose of 6 mg administered three times every four weeks during the loading phase based on the previous clinical phase 3 program in which 1088 subjects with nAMD received brolucizumab (RTH258-C001 - HAWK and RTH258-C002 - HARRIER). The nAMD study results regarding q12w/q8w maintenance dosing interval support stretching the interval between injections during the maintenance-phase to reduce the treatment burden (see [Section 1.1](#)).
- CRTH258AUS04 (MERLIN) is a two-year, multicenter, randomized, double masked, phase IIIa study evaluating brolucizumab 6 mg q4w versus aflibercept 2 mg q4w in patients with nAMD with persistent fluid. Review of the 52-week FIR led to an urgent safety communication based on an increased incidence of intraocular inflammation (IOI) and related adverse events including retinal vasculitis (RV), and retinal vascular occlusion (RO) in patients with q4w dosing with brolucizumab beyond the “loading phase”. IOI including RV, and RO were reported at a higher frequency in brolucizumab 6 mg q4w when compared to aflibercept 2 mg q4w (IOI: 9.3% vs. 4.5% of which RV: 0.8% vs. 0.0%, RO: 2.0% vs. 0.0%, respectively). Therefore, the protocol contains the note to discontinue subjects from study treatment who require treatment every 4 weeks.

- The route of administration is an intravitreal injection as for all anti-VEGF treatments currently approved for the treatment of nAMD.
- Study duration of 52 weeks allows for one initial injection followed by four complete 12-week intervals to evaluate effect of non-loading on long-term efficacy and safety.

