9.1.1 Discontinuation of study treatment

Discontinuation of study treatment for a subject occurs when study treatment is stopped earlier than the protocol planned duration and can be initiated by either the subject or the investigator.

The investigator must discontinue study treatment for a given patient if, he/she believes that continuation would negatively impact the subject's well-being.

Study treatment must be discontinued under the following circumstances:

- Subject decision
- Pregnancy (see [Section 8.4.2](#) and [Section 10.1.4](#))
- Use of prohibited treatment (see [Section 6.2.2](#))
- Any situation in which continuation with study treatment might result in a safety risk to the subject
- Unsatisfactory therapeutic effect, e.g. a subject requires injections more frequently than every 8 weeks after the loading phase (week 8, loading arm) or baseline (non-loading arm).
- Subjects develop intraocular inflammation, retinal vasculitis and/or retinal vascular occlusion

If discontinuation of study treatment occurs, the investigator should make a reasonable effort to understand the primary reason for the subject's premature discontinuation of study treatment and record this information on the appropriate eCRF page.

Subjects who prematurely discontinue study treatment for any reason, except for withdrawal of consent (refer to [Section 9.1.2](#)), should continue in the study with all the scheduled visits and assessments (except disease stability assessment, administration of study treatment, post-injection assessment and adherence to prohibited medication list) until EOS. These patients can be switched to standard of care anti-VEGF IVT as per investigator's discretion. Any IVT injection is contraindicated in subjects with active intraocular or periocular infections and in subjects with active intraocular inflammation; therefore, the investigators must verify that these conditions are not present in the study eye prior to every injection.

Subjects who decide not to participate in the study further should NOT be considered withdrawn from the study, UNLESS they withdraw their consent (see [Section 9.1.2](#)). **Where possible, subjects should return for the EOS visit assessments to be performed as scheduled in Table 8-1.**

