12.5.2 Safety endpoints

The secondary safety objective and endpoint of this study is as follows:

To evaluate the safety and tolerability of brolucizumab

- Incidence of ocular and non-ocular AEs up to week 52

There are no formal safety hypotheses in this study. For all safety analyses, the safety set will be used. All listings and tables will be presented by treatment arm.

Safety endpoints are based on the variables from safety assessments which include:

- Extent of exposure
- Adverse events
- Ophthalmic examinations

- Vital signs

Safety summaries (tables, figures) include only data from the on-treatment period with the exception of baseline data which will also be summarized where appropriate (e.g. change from baseline summaries). In addition, a separate summary for death including on treatment and post treatment deaths will be provided. In particular, summary tables for adverse events (AEs) will summarize only on-treatment events, with a start date during the on-treatment period (treatment-emergent AEs). A separate summary table will be provided for AEs of study eye, fellow eye and non-ocular AEs.

The on-treatment period lasts from the date of first administration of study treatment to 30 days after the last administration of study treatment (EOT) or EOS whichever is the latest.

Adverse events

A treatment-emergent adverse event is defined as any adverse event that develops after initiation of the study treatment or any event already present that worsens following exposure to the study treatment. Only treatment-emergent adverse events will be presented in the summary tables.

All information obtained on adverse events will be displayed by treatment arm and subject.

The number (%) of subjects with treatment emergent adverse events (events started after the first dose of study medication or events present prior to start of treatment but increased in severity based on preferred term) will be summarized in the following ways:

- by treatment, primary system organ class and preferred term.
- by treatment, primary system organ class, preferred term and maximum severity.
- by treatment, standardized MedDRA Query (SMQ) and preferred term.

Separate summaries will be provided for study medication related adverse events, death, serious adverse events, other significant adverse events leading to discontinuation.

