2.8 Safety analyses

The secondary safety objective and endpoint of this study is as follows:

To evaluate the safety and tolerability of brolucizumab

- Incidence of Ocular and Non-ocular AEs up to week 52

There are no formal safety hypotheses in this study. All safety analyses will be performed using the Safety Set. All listings and tables will be presented by treatment arm.

Safety endpoints are based on the variables from safety assessments which include:

- Extent of exposure
- Adverse events
- Ophthalmic examination and imaging
- Vital signs

Safety summaries (tables, figures) include only data from the on-treatment period with the exception of baseline data which will also be summarized where appropriate (e.g. change from baseline summaries). In addition, a separate summary for death including on treatment and post treatment deaths will be provided. In particular, summary tables for adverse events (AEs) will summarize only on-treatment events, with a start date during the on-treatment period

(treatment-emergent AEs). Separate summary tables will be provided for AEs of study eye, fellow eye and non-ocular AEs.

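### Study-eye adverse events after a switch to another anti-VEGF count as on-treatment under the brolucizumab regimen, and no planned table separates them

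*SAP*

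**What the plan says.** **The window.** SAP 2.1.1 states: "The term study treatment is used for Brolucizumab 6 mg/0.05 mL". Its on-treatment period starts at the first administration and lasts "to 30 days after the last administration of study treatment (EOT) or EOS whichever is the latest". Protocol 12.5.2 has the same rule: "The on-treatment period lasts from the date of first administration of study treatment to 30 days after the last administration of study treatment", or to EOS if that is later.

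**Patients who stop.** Under Protocol 9.1.1, patients who stop study treatment without withdrawing consent "should continue in the study with all the scheduled visits and assessments" until EOS. They no longer have to follow the prohibited-medication list, and the protocol adds: "These patients can be switched to standard of care anti-VEGF IVT", at the investigator's discretion. New treatments and adverse events are still collected for them.

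**The tables.** Protocol 12.5.2 states: "Safety summaries (tables, figures) include only data from the on-treatment period", with baseline data as the exception. SAP 2.8 and 2.8.1 repeat this and summarise, by arm, every adverse event that starts in the window.

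**A different boundary elsewhere.** Protocol 10.1.1 continues AE monitoring until 30 days after the last study injection. SAP 5.1.2 imputes or caps incomplete AE end dates at last injection plus 30 days.

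**The concern.** The secondary safety objective concerns the safety and tolerability of brolucizumab. After a switch, the study eye receives another drug through further intravitreal injections. Protocol 4.5 itself notes that intravitreal injections in general have been associated with endophthalmitis, retinal detachment and acute pressure rises. Events of this kind that start after the switch still appear in the column of the brolucizumab regimen under which the patient is analysed.

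The exposure summary in SAP 2.4.1 counts only injections of the investigational drug. For a switched patient, the exposure and adverse event tables therefore describe different periods. With about 25 patients per arm, a single event moves an incidence visibly, and a reader of the tables could not tell whether it came before or after the switch.

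**Working it through.** The documents give no figure on this point, so there is none to reproduce. The check has three parts.

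**1. Does any planned output separate events after a switch?**

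| Output | Separates them? |
|---|---|
| Incidence tables: overall, SOC/PT, severity, SAE (SAP 2.8, 2.8.1) | No. Any event starting in the window is counted. |
| Drug-related and causality summaries (SAP 2.8.1) | In part. Protocol 10.1.1 rates relationship to study treatment or to the ocular injection procedure. There is no category for another drug, and the procedure category is not limited to brolucizumab injections. |
| Listing of AEs after the on-treatment period (SAP 2.8.1) | No. It begins after the later of the two end dates. |
| Table for events of special interest | None. SAP 2.8.1.1 defines no such events, although Protocol 10 names intraocular inflammation, vasculitis and occlusion as such. |
| Subject-level listings of AEs, injections and concomitant medication (SAP 2.4, 2.8.1) | Only by hand. |

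**2. How much time is involved?** Inputs: EOS at week 52 = day 364 from first injection; last brolucizumab at week w = day 7w. Days counted as on-treatment beyond last dose plus 30 days = max(0, 364 − (7w + 30)).

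| Last dose | Last dose + 30 | Days beyond it, to day 364 | Share of window |
|---|---|---|---|
| Baseline | day 30 | 334 | 92% |
| Week 8 | day 86 | 278 | 76% |
| Week 24 | day 198 | 166 | 46% |
| Week 36 | day 282 | 82 | 23% |
| Week 44 | day 338 | 26 | 7% |
| Week 48 | day 366 | 0 | 0% |

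Patients who stay on schedule are almost unaffected. These days stand in for post-switch time and do not equal it. With a last dose at week 8, a first other injection at week 12 gives 364 − 84 = 280 post-switch days, and one at week 20 gives 364 − 140 = 224.

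The documents give no rate of stopping and switching. Assume that 5% to 30% of 50 patients (2.5 to 15) stop, with a last dose between week 24 and week 8, out of 50 × 364 = 18,200 follow-up days:

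- low end: 2.5 × 166 = 415 days, 415/18,200 = 2.3%
- high end: 15 × 278 = 4,170 days, 4,170/18,200 = 22.9%

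One patient with an event in an arm of 25 is 1/25 = 4 percentage points.

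**3. Do the date rules agree with the window?** Take a last study injection on day 56 and an event that starts on day 200. It is before day 364, so it is tabulated. If its end date is missing, SAP 5.1.2 sets the end to 56 + 30 = day 86, which is 114 days before it starts. An end date known only to a later month is capped at the same day. The SAP thus uses two boundaries for the same events.

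**The case against.** The best defence is that the window is deliberate. The safety endpoint is adverse events up to week 52, protocol and SAP give the same definition, and follow-up to EOS after stopping is planned. Treatment-emergent is a statement about timing, and attribution has its own summaries. In about 50 patients the listings can be read by hand. All of this stands, and it is why neither the definition nor the week-52 tables should change.

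A reader might go further and infer that the plan attributes the other drug's harms to brolucizumab. The documents do not support that. Such an event enters the drug-related table only if the investigator relates it to brolucizumab.

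A reader might also want the on-treatment period to end at the switch. Because safety summaries are limited to on-treatment data, that would truncate all of them, including non-ocular events and vital signs. It could also move late brolucizumab reactions out of the table; Protocol 1.1 describes an immune-mediated mechanism for vasculitis and occlusion.

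Nor does the rule empty the post-treatment category. The phrase "In addition, a separate summary for death including on treatment and post treatment deaths will be provided" concerns deaths only. After a week-48 dose, SAE reporting (Protocol 10.1.3) runs to day 336 + 60 = 396, 30 days beyond the window's end at day 366.

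The defence does not supply a table that shows study-eye incidence before any other anti-VEGF was given. The causality summaries and the post-period listing do not provide one either.

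**Conclusion.** The concern holds as a gap in presentation. For patients who stop brolucizumab early and switch, timing-based incidence tables mix time on brolucizumab with time on another drug, and nothing planned separates the two. It is worth correcting because the remedy is cheap.

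The size per patient follows from the dates: 278 of 364 days (76%) for a last dose at week 8, falling to none at week 48. The total is unknown; the 2% to 23% range rests on assumed stopping rates and dates. The effect on event counts is smaller than the time suggests, because tables count patients with at least one event. A repeat under the same preferred term adds nothing to that row.

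Two stronger inferences are not supported. First, one could apply the comparator rate in Protocol 4.2 ("IOI: 9.3% vs. 4.5% of which RV: 0.8% vs. 0.0") to the off-brolucizumab weeks: 52 − (8 + 30/7) = 39.7 weeks, and 4.5% × 39.7/52 = 3.4% per patient. That rate belongs to four-weekly aflibercept in another trial, and nothing says switched patients are dosed that way. Even so, 2.5 to 15 switched patients would give only 0.09 to 0.51 events. Second, the rule on needing injections more often than every 8 weeks starts at baseline in one arm and at week 8 in the other, so switching could differ by arm. The documents contain nothing to show that it does. Switching is optional, and patients may also stop for other reasons, including their own decision.

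**What to change.** 1. Leave the on-treatment definition and the week-52 AE tables unchanged.
2. Add one table of study-eye ocular adverse events by arm, split into events starting before and events starting on or after the first non-study anti-VEGF injection in the study eye. Patients who never switch have all their events in the first part. Show both parts side by side, with the number of switched patients, and state that events soon after the switch may still be due to brolucizumab.
3. In SAP 5.1.2, replace last injection plus 30 days in the end-date rules with the end of the on-treatment window in SAP 2.1.1, so that no imputed end precedes its start.
4. Reconcile the 30-day AE monitoring statement in Protocol 10.1.1 with the continued visits and AE collection in Protocol 9.1.1. Read alone, the former would leave late non-serious events unevenly captured.

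The cost is one derived date, taken from treatment data already collected, one extra table and a short edit to the date rules. The counts after the switch will be sparse, so the new table is for description only.

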2.7.2 Statistical hypothesis, model, and method of analysis

Secondary endpoints will be analyzed using adequate descriptive statistics, if not otherwise specified. Details on planned analyses are listed in the table below.

Table 2 Endpoints and statistical method

Endpoints for secondary objectives	Statistical method
1.Treatment interval	
1.1. Mean treatment interval (overall as well as per study group comparing treatment intervals from week 8 to week 52 in the study vs. 24 weeks to baseline prior to enrollment)	Descriptive analysis of injection intervals (weeks): Summary statistics (n,mean, SD, min, median, max) for - Mean treatment interval from week 8 to week 52 - Mean treatment interval within 24 weeks prior to baseline. - Last treatment interval under observation Box Plot for “last treatment interval under observation”. Stacked Bar Chart for patients on q8w and q12w by visit (last documented DAA).

1.2. Rate of patients (overall and per group) with prolonged interval compared to mean treatment interval in last 24 weeks to baseline prior to enrollment

- **Frequencies and percentages (n(%))** for total FAS and both treatment arms.

- **Logistic regression model**

Dependent variable: interval prolongation* (Y/N)

Factors:

- treatment arm
- baseline BCVA
- age

Odds-ratio, 95% CI and p-value.

Estimates for , non-loading arm, loading arm and difference (non-loading – loading).

* Prolongation is calculated by comparing the “mean treatment interval in last 24 weeks prior to first brolucizumab injection” (defined in section 2.3.2) with the time interval between the last two brolucizumab injections. Patients with only one injection in treatment period are calculated as non-responders (no interval prolongation).

2. Maintenance of q12w intervals

2.1. Comparison of proportions of patients maintained at a q12w interval at week 52 between the two arms

- **Frequencies and percentages (n(%))** for total FAS and both treatment arms.

- **Logistic regression model**

Dependent variable: “q12w” (Yes/No): “DAA maintained at q12w from baseline / upload to week 52”

Factors:

- treatment arm
- baseline BCVA
- age

Odds-ratio with 95% CI and p-value.

Patients who discontinued treatment prior to week 52 are calculated as non-responders.

2.2. Distributions of patients at q8w/q12w intervals from baseline to week 52

Descriptive statistics for treatment regimens:
Frequencies and percentages (n (%)) by visit

3. Functional Outcomes

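### Endpoint 1.1 compares on-study with pre-study treatment intervals but has no within-patient change with SD or CI, and no rule for patients with fewer than two injections from week 8

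*SAP*

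**What the plan says.** The first secondary objective in SAP 1.2 is "To evaluate treatment interval prolongation compared to previous treatment". Endpoint 1.1 in Table 2 of SAP 2.7.2 is worded as a comparison: "comparing treatment intervals from week 8 to week 52 in the study vs. 24 weeks to baseline prior to enrollment". The method listed for it is "Descriptive analysis of injection intervals (weeks): Summary statistics (n,mean, SD, min, median, max) for" three quantities:

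- the on-study mean interval;
- the pre-study mean, given as "Mean treatment interval within 24 weeks prior to baseline";
- the last interval under observation.

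A box plot of the last interval and a bar chart of q8w/q12w status by visit complete the entry. No within-patient difference is listed.

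SAP 2.1.1 gives the two formulas. The on-study numerator is "last injection – first injection from week 8 on", and it is "divided by (number of injections from week 8 to week 52 -1". A footnote adds that "the first injection from week 8 on could be at week 8 or later". The pre-study mean is the time from the first anti-VEGF injection in the 24-week window to the first brolucizumab injection, "divided by number of injections within 24 weeks prior to first brolucizumab injection". That denominator has no minus 1. SAP 2.7.3 says that missing secondary values are not replaced.

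**The concern.** Two things look incomplete.

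First, the endpoint asks how far the interval changed when the same patients switched regimen. Two separate means with two separate SDs do not give the precision of that change, because the within-patient correlation is not reported. This is true even if every patient has both values.

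Second, the two formulas do not apply to the same patients. One pre-study injection is enough for a pre-study mean, whereas an on-study mean needs two injections from week 8. Protocol 9.1.1 requires study treatment to stop in several circumstances, among them intraocular inflammation and a need for injections more often than every 8 weeks, so early stopping is plausible. Such a patient normally remains in the FAS (SAP 2.2; SAP 5.5 removes only those never treated, without a post-baseline visit or without consent). The patient would then count in the pre-study mean and not in the on-study mean.

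At stake is whether the first secondary objective yields a mean prolongation, with its uncertainty, in a clearly identified group of patients.

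**Working it through.** The documents state no numerical figure for this endpoint (their precision figures concern BCVA), so there is none to reproduce. The check applies the SAP 2.1.1 formula to example schedules and then sizes the consequences.

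**1. On-study formula.** Value = (last − first injection from week 8) / (number of injections from week 8 to 52 − 1).

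| Injections (weeks) | From week 8 | Value |
|---|---|---|
| Loading, full q12w: 0, 4, 8, 20, 32, 44 | 4 | 36/3 = 12.0 |
| Non-loading, full q12w: 0, 12, 24, 36, 48 | 4 | 36/3 = 12.0 |
| Non-loading, q8w after week 12: 0, 12, 20, 28, 36, 44 | 5 | 32/4 = 8.0 |
| Loading, stops after week 8: 0, 4, 8 | 1 | 0/0 |
| Non-loading, stops after week 12: 0, 12 | 1 | 0/0 |
| Loading, stops after week 4: 0, 4 | 0 | no dates, denominator −1 |
| Non-loading, stops after baseline: 0 | 0 | no dates, denominator −1 |

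The formula works for anyone with two or more injections from week 8. On q12w, that point is reached at week 20 in the loading arm and week 24 in the non-loading arm.

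**2. Pre-study formula.** Protocol 5.1 requires continuous treatment at intervals of 26 to 86 days before baseline. The 24-week window is 168 days, longer than 86, so every eligible patient should have at least one injection in it and therefore a pre-study mean.

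**3. Does the rule in endpoint 1.2 fill the gap?** Endpoint 1.2 counts patients with only one injection in the treatment period as not prolonged. The rule is written for 1.2 and counts injections over the whole period. The loading patient with injections at weeks 0, 4 and 8 has three, so falls outside it, and has a last interval of 4 weeks for 1.2. The non-loading patient with injections at 0 and 12 has two, and a last interval of 12 weeks. Both are 0/0 in 1.1.

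**4. Size of the mismatch.** Let N be the number in the FAS and k the number without an on-study mean. Suppose the pre-study mean of those k is d weeks shorter than that of the rest, m. Then:

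- pre-study mean in all patients = m − kd/N;
- gap between the two separate means = gap in patients with both values + kd/N.

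N = 50 is the expected recruitment; k and d are assumptions.

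| k of 50 | d = 2 weeks | d = 4 weeks |
|---|---|---|
| 0 | 0 | 0 |
| 1 | 2/50 = 0.04 | 4/50 = 0.08 |
| 2 | 4/50 = 0.08 | 8/50 = 0.16 |
| 5 | 10/50 = 0.20 | 20/50 = 0.40 |

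With 23 per group (N = 46) the largest entry becomes 20/46 = 0.43. If d is negative, the sign reverses.

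**5. Precision that the separate summaries cannot give.** Assume the same SD, s, in both periods and correlation r. The SD of the difference is s × √(2(1 − r)), and the 95% half-width with 50 pairs is 2.01 × s × √(2(1 − r)) / √50. With s = 2 weeks:

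- r = 0: 2.01 × 2 × 1.414 / 7.071 = 0.80 weeks;
- r = 0.5: 2.01 × 2 × 1 / 7.071 = 0.57 weeks.

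The same two printed SDs are compatible with both answers. For s from 1.5 to 3 weeks and r from 0 to 0.5, the half-width runs from 0.43 to 1.21 weeks. These SDs and correlations are assumed, not taken from the documents.

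**The case against.** A reader might infer that prolongation has no paired estimate at all. That goes too far. Endpoint 1.2, under the same objective, compares each patient's own pre-study mean with that patient's last on-study interval. It reports frequencies overall and by arm, and a logistic regression with an odds ratio and 95% CI. What is missing is only the continuous mean change.

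A reader might also infer that early stoppers vanish unseen. Each summary in 1.1 prints n, so unequal denominators would show, and SAP 2.3.1 tabulates treatment discontinuation with reasons. An undefined value would naturally be treated as missing under SAP 2.7.3. What the tables would not show is which discontinuations left a patient without an on-study mean.

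The third tempting inference is that apparent prolongation will be inflated. The documents do not support a direction. Besides a need for frequent injections, Protocol 9.1.1 lists inflammation, subject decision, pregnancy and prohibited treatment as reasons to stop, and nothing ties those to a short prior interval. Nor is there a count. The 10% drop-out in Protocol section 3 belongs to the 490-patient plan and is not the rate of stopping before a second injection from week 8.

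Finally, the trial is now purely descriptive, two means by arm arguably meet the endpoint's wording, and in patients with both values the difference of the means equals the mean difference. This stands for the point estimate but not for its SD or CI. Protocol 12.5.1 expressly allows confidence intervals for group comparisons of secondary endpoints, so an interval here fits the descriptive scope.

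**Conclusion.** The point holds as a modest and inexpensive improvement. Two parts follow from the text alone: endpoint 1.1 lists no within-patient change with SD or CI, and the on-study formula is undefined with fewer than two injections from week 8, with no rule for that case.

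The mismatch between the two groups of patients is conditional. It arises only if at least one FAS patient has fewer than two injections from week 8, and it is zero otherwise. Its size of about 0.04 to 0.4 weeks rests on assuming 1 to 5 such patients among 50 and a prior mean 2 to 4 weeks shorter, and its sign rests on that second assumption. The missing paired precision does not depend on anyone stopping early. Neither gap affects the primary endpoint.

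**What to change.** In SAP Table 2, endpoint 1.1:

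- Add the within-patient difference (week 8 to 52 mean minus pre-study mean) with n, mean, SD and 95% CI, overall and by arm, in patients with both values.
- Show the pre-study mean for that same subset beside the full-FAS pre-study summary, which is kept.
- State that patients with fewer than two injections from week 8 have no on-study mean, and count them by arm and by reason.

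The cost is a few lines of SAP text and a few table rows, with no new data. The downside is that the paired estimate describes only patients with at least two injections from week 8. Selection therefore remains, but the count makes it visible.
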